9.10.7.2. Clinical Benefit Rate

Clinical benefit rate (CBR) is defined as the proportion of participants who have a response (CR or PR) or stable disease (SD). CBR will be tabulated at Week 25, 49, and 73. CBR will be calculated among participants in the ITT Set. The denominator will include all participants in the ITT Set who have reached the Week 25, 49 or 73 timepoint or have discontinued from the study prior to that timepoint.

Clinical benefit at Week 25, 49 or 73 will be derived based on reported overall tumor responses at different evaluation timepoints from the date of first dose up to and including the Week 25, 49 or 73 timepoint.

Clinical benefit status at Week 25, 49, or 73:

• Clinical Benefit (CB):

- at least 1 CR or PR result, up to and including the specific timepoint of interest
- only SD or NE results obtained up to the specific timepoint of interest and a SD result at the specific timepoint of interest
- No Clinical Benefit (NCB): Not meeting the above definition for CB

These exploratory analyses will be conducted based on RECIST v1.1, TVS and mRECIST from IRR, and based on investigator assessment per RECIST v1.1.

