9.10.2. Primary Endpoint

Objective response rate (ORR) per RECIST v1.1 at Week 25 is defined as the proportion of participants with a CR or a PR as the Week 25 Tumor Response (as defined in Table 2) based on IRR per RECIST v1.1. ORR at Week 25 will be compared between the 2 treatment groups using a two-sided Cochran-Mantel-Haenszel (CMH) test stratified by the randomization stratification factors. The test will be performed at a 0.05 alpha level on the ITT Set. A 95% CI for the proportion in each arm using the Clopper-Pearson method as well as the difference in proportion and its associated Wald 95% CI will be presented. A Fisher's exact test and an exact 95% CI for the difference in proportion will be provided as a sensitivity analysis.

No confirmation (ie, CR or PR at the subsequent MRI assessment) will be required for a CR or PR per RECIST v1.1 as this is a randomized study. Complete and partial response will define response for the primary endpoint and additional efficacy analyses.

Determination of an overall response for each timepoint is based on the combination of responses for target lesions, and the presence or absence of one or more new lesions per RECIST v1.1. For this study, determination of the tumor response status for each participant in Part 1 with respect to the primary efficacy endpoint is shown in Table 2 below. All unscheduled assessments prior to Week 25 will be incorporated into the determination of ORR at Week 25 in a similar fashion as Week 13. End of Part 1 scans will be windowed according to Section 8.3. If a participant is missing a scan at Week 25, then they will be considered a non-responder.

Table 2: Definitions of Response for the Primary Efficacy Endpoint

Timepoint Response at Week 13	Timepoint Response at Week 25	End of Part 1 (Week 25) Tumor Response Status
		(Primary Efficacy Endpoint)
CR or PR	CR	Response (CR)
CR or PR	PD	Non-response (PD)
PR	Non-CR/non-PD/non-NE ^a	Response (PR) ^b
SD	CR or PR	Response (CR or PR)
SD	SD	Non-response (SD)
SD	PD	Non-response (PD) ^c
CR, PR, SD, and NE	NE	Non-response (NE)
PD	Any	Non-response (PD)
NE	CR or PR	Response (CR or PR)
NE	SD or PD	Non-response (SD or PD)

Abbreviations: CR=complete response; NE=not evaluated or unevaluable; PD=progressive disease; PR=partial response; SD=stable disease.

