9.10.7.1. Objective Response Rate at Specific Timepoints

Response at a specific timepoint will be derived based on reported overall tumor responses at different evaluation timepoints from the date of first dose up to and including the specific timepoint assessment. Response at Week 25 will be determined based on Section 9.10.2 and responses at other timepoints will be determined based on:

- Complete response (CR): at least one CR reported up to and including the specific timepoint assessment and the specific timepoint assessment is not Progressive Disease or NE
- Partial response (PR): at least one PR but no CR reported up to and including the specific timepoint assessment and the specific timepoint assessment is not Progressive Disease or NE
- Stable disease (SD): at least one SD but no CR nor PR reported up to and including the specific timepoint assessment and the specific timepoint assessment is not Progressive Disease or NE
- Progressive disease: Progressive Disease at the specific timepoint assessment or Progressive Disease before the specific timepoint regardless of response status at the specific timepoint
- Not Evaluable (NE): no Progressive Disease before the specific timepoint and the specific timepoint assessment is NE or missing

ORR at Week 25, 49 or 73 is defined as the proportion of participants with Response at the specific time point being either CR or PR. The denominator for will include all participants in the ITT Set who have reached the Week 25, 49 or 73 timepoint or have discontinued from treatment or the study prior to that timepoint. An exact 95% confidence interval (CI) on the rates of response will also be presented.

These exploratory analyses will be conducted based on RECIST v1.1, TVS and mRECIST from IRR, and based on investigator assessment per RECIST v1.1.

Swimlane plots will present objective response and time to response duration for individual participants where time to response is defined as date of first CR or PR - treatment start date + 1.

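### Clinical benefit 'at' Weeks 25, 49 and 73 counts any CR or PR up to that week with no PD or NE condition, so a participant classed as PD or NE at that week can be tabulated as having benefit (exploratory rate only)

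*SAP*

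**What the plan says.** SAP 9.10.7.2 defines the clinical benefit rate (CBR) as the proportion of participants with a response or stable disease. It derives a "Clinical benefit status at Week 25, 49, or 73" by two routes:

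- CR/PR route: "at least 1 CR or PR result, up to and including the specific timepoint of interest".
- SD route: "only SD or NE results obtained up to the specific timepoint of interest and a SD result at the specific timepoint of interest".

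The only other category, No Clinical Benefit, is a remainder: "Not meeting the above definition for CB". Nothing else in the section refers to PD or to an NE scan at the timepoint.

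The neighbouring rules for response at the same weeks do refer to them. In SAP 9.10.7.1, CR, PR and SD each require that the assessment at the timepoint is not PD or NE. The PD category includes "Progressive Disease before the specific timepoint regardless of response status at the specific timepoint", and the NE category is "no Progressive Disease before the specific timepoint and the specific timepoint assessment is NE or missing". For Week 25, 9.10.7.1 defers to 9.10.2. There, Table 2 makes PD at Week 13 or Week 25 a non-response and NE at Week 25 a non-response, and the text treats a missing Week 25 scan as a non-response.

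CBR is to be produced from IRR data by RECIST v1.1, TVS and mRECIST, and from investigator RECIST v1.1. SAP 9.10.7 says that exploratory endpoints are not formally tested, although nominal p-values may be given.

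**The concern.** Under the CR/PR route, benefit cannot be lost once a single CR or PR is recorded. A participant with PR at Week 13 and PD at Week 25 is a non-responder with PD in the Week 25 ORR table, but has clinical benefit at Week 25, and again at Weeks 49 and 73, in the CBR table. A response first seen after PD also counts.

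The two routes within 9.10.7.2 follow different time logic. The SD route excludes any PD up to the timepoint and requires SD at the timepoint itself; the CR/PR route requires neither freedom from PD nor an evaluable scan.

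At stake is the meaning of a descriptive table. The difference between CBR and ORR at a given week would no longer be the proportion with SD. Relative to the timepoint rules, the CBR numerator can only be raised.

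**Working it through.** The plan states no figure for CBR, so there is none to reproduce. The check applies the rules to every possible pattern.

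**Inputs.** Response categories CR, PR, SD, PD, NE (SAP Table 2); scheduled Part 1 scans at Weeks 13 and 25 (protocol Table 1); planned arms of about 80 and 40 (SAP 5). Unscheduled scans are left out.

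**Step 1: patterns counted as benefit now.** There are 5 × 5 = 25 Week 13/Week 25 patterns.
- With at least one CR or PR: 25 − 3 × 3 = 16.
- By the SD route: SD-SD and NE-SD = 2.
- Total: 16 + 2 = 18. The remaining 7 are No Clinical Benefit.

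**Step 2: compare with the other rules.** Six of the 18 are PD or NE under Table 2:

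| Week 13-Week 25 | CBR status | Table 2 | Responder at least once by Week 25 (9.10.2 sensitivity) | BOR (9.10.4.1) |
|---|---|---|---|---|
| CR-PD | Benefit | PD | Yes | CR |
| PR-PD | Benefit | PD | Yes | PR |
| PD-CR | Benefit | PD | Yes | PD |
| PD-PR | Benefit | PD | Yes | PD |
| CR-NE | Benefit | NE | Yes | CR |
| PR-NE | Benefit | NE | Yes | PR |

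**Step 3: look for conflicts the other way.** The 7 No Clinical Benefit patterns are SD-PD, SD-NE, PD-SD, PD-PD, PD-NE, NE-PD and NE-NE. Table 2 classes all of them as PD or NE, so there are 0 reverse conflicts.

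**Step 4: apply the amended CR/PR route.** Requiring no PD at or before Week 25, and a Week 25 scan that is not NE or missing, removes exactly the six: 18 − 6 = 12 patterns, with 0 conflicts with Table 2. CR-PR and CR-SD, which have no row in Table 2, remain benefit.

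**Step 5: apply the cumulative alternative.** Defining benefit by Week 25 as a BOR of CR, PR or SD gives 3 × 5 = 15 patterns with CR, PR or SD at Week 13, plus 3 with NE then CR, PR or SD. The total is again 18, but PD-CR and PD-PR leave while SD-PD and SD-NE enter.

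**Step 6: effect per participant.**
- Vimseltinib arm: 1/80 = 1.25 points, if all 80 are in the denominator.
- Placebo arm at Week 25: 1/40 = 2.5 points, if all 40 are.
- Pooled on-vimseltinib display (second approach in SAP 9.10.7), if used for CBR and all 120 are in the denominator: 1/120 = 0.83 points.

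The documents give no rate of progression or of NE scans after response, so no total is estimated.

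**The case against.** The strongest reply is that the rule is explicit, reproducible and has a precedent in the SAP. The 9.10.2 sensitivity analysis already counts anyone who responded at least once by Week 25, with no PD or NE condition, and all six patterns are responders there. Under BOR, four of the six are CR or PR. A reader might infer that a cumulative reading is impossible; the documents do not support that. What remains is that the sensitivity analysis is labelled 'by', CBR is labelled 'at', and the SD route is tied to the timepoint. The present rule is therefore neither a timepoint measure nor a consistent cumulative one, and PD-CR and PD-PR exceed even BOR.

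Table 2 footnote c, which does not accept SD of shorter duration, could explain why the SD route is tied to the timepoint. The SAP does not say so, and it would not explain ignoring PD in the CR/PR route.

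Footnote b treats a PR as ongoing until progression is documented, so counting an earlier responder with an NE scan is defensible. This stands: the NE condition is a convention for consistency with ORR, not a necessity.

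Response after PD should be limited on IRR RECIST, because IRR-confirmed PD in Part 1 ends vimseltinib treatment or opens crossover for placebo participants (protocol 10.5). It is not excluded. Scans are not read centrally in real time unless the investigator suspects progression (protocol 11.9.13.1), and PD by TVS or mRECIST is not a stated reason to discontinue.

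**Conclusion.** The point holds as an internal inconsistency in one exploratory rate. The PD part is a definite conflict with the SAP's own timepoint rules; the NE part conflicts with the same rules but rests on a convention that CBR is not bound to adopt. The direction is upward only. The size is 1.25 or 2.5 points per affected participant by randomized arm, and less in a pooled display, assuming planned numbers and full denominators.

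A reader might infer from 6 of 18 that a third of reported benefit would be spurious. The documents do not support that: the patterns are not equally likely and no frequencies are given. Nor does the point reach the main results. CBR is in none of the SAP's endpoint lists and is not formally tested. The primary, key secondary, BOR and DOR analyses use their own rules, and loss of response stays visible in timepoint ORR, DOR and the listings. The change is worth making because it is cheap, not because a conclusion depends on it.

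**What to change.** Keep the existing CR/PR requirement in the first bullet of 9.10.7.2 and add two conditions: no Progressive Disease at or before the timepoint, and an assessment at the timepoint that is not NE or missing. This applies at all three weeks and does not depend on Table 2.

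The PD condition is the necessary correction. The NE condition aligns CBR with the ORR rules and the SD route. Its cost is that an earlier responder whose scan at that week is NE or missing counts as no benefit. If the sponsor prefers not to adopt it, the SAP should say that such participants keep their benefit status.

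If a cumulative measure is intended, label it 'by Week X' and define both routes as a BOR of CR, PR or SD up to that week under 9.10.4.1. Changing only the CR/PR route would leave the SD route tied to the timepoint. The cost is that the rate no longer describes status at the week, and that SD followed by PD or NE would newly count.

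Either way the change is confined to one definition. With the amended bullet, reported CBR can only stay the same or fall.

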9.10.7.3. Tumor Size Over Time

Observed value, change from baseline and percent change from baseline in tumor size will be summarized over time.

The largest percentage change (in absolute value) in tumor size, up to week 25 and through all available follow-up, will be summarized in waterfall plots for RECIST v1.1.

9.10.7.4. Tissue Damage Score

Observed value and change from baseline in TDS components will be summarized over time.

9.10.7.5. Range of Motion Over Time

Observed value and change from baseline in active ROM of the affected joint, relative to a reference standard, will be summarized over time, including Week 49 as a timepoint of interest.

Observed value and change from baseline in active ROM of the affected joint, relative to the contralateral joint, will be summarized over time, including Week 25 and Week 49 as timepoints of interest.

Observed value and change from baseline in passive ROM of the affected joint, relative to a reference standard and to the contralateral joint, will be summarized over time, including Week 25 and Week 49 as timepoints of interest.

9.10.7.6. Clinician and Patient Global Impression of Change and Severity

Clinician Global Impression of Change (CGIC) and of Severity (CGIS) as well as Patient Global Impression of Change (PGIC) and of Severity (PGIS) will be summarized over time, including Week 13, Week 25 and Week 49 as timepoints of interest.

- Observed value will be summarized for CGIC and PGIC, as well as response in CGIC and PGIC, defined as an answer of "Very Much Improved" or "Much Improved"
- Observed value and change from baseline will be summarized for CGIS and PGIS.

9.10.7.7. Brief Pain Inventory

The analysis performed for BPI-30 response described in Section 9.10.3.6 will be replicated using BPI average pain NRS.

Observed value and change from baseline in BPI worst pain NRS and average pain NRS will be summarized over time.

9.10.7.8. Burden of Side Effects – GP5 from FACT-G

GP5 "burden-of-side-effects" question from the Functional Assessment of Cancer Therapy-General (FACT-G) will be summarized over time, including Week 25 as a timepoint of interest. This will include count and proportion of participants burdened by side effects defined as those with a response of 3 ("quite a bit") or 4 ("very much").

9.10.7.9. Worst Stiffness NRS Over Time

Observed value and change from baseline in worst stiffness NRS will be summarized over time.

9.10.7.10. EQ-VAS Over Time

Observed value and change from baseline in EQ-VAS will be summarized over time.

9.10.7.11. PROMIS-PF Over Time

Observed value and change from baseline in PROMIS-PF will be summarized over time.

9.10.8. Other Exploratory Analyses

Pharmacokinetic concentration data will be summarized over time and a listing will be provided.

Other than basic data summaries, the analyses for the following items will be described in documents separate from the CSR.

Pharmacokinetics

• Correlation of PK with efficacy and/or safety

Pharmacodynamics

• Effects of pharmacodynamics in relation to safety or efficacy

Pharmacogenomics

• Germline polymorphisms in genes involved in the metabolism or disposition of vimseltinib or related to safety and/or efficacy

9.11. Safety Analysis

All safety analyses will be conducted on the SAF. If there are both local and central assessments in the same nominal visit, then the central assessment will be used for analyses. The safety data will be summarized following two different approaches. The first approach will be limited to data from Part 1 and will focus on comparisons between participants who received vimseltinib versus participants who received placebo during this period. The second approach will combine data from both Part 1 and Part 2 (including extension period) and will focus on the observations and assessments while participants are receiving vimseltinib. Therefore, in this second approach, participants randomized to Placebo in Part 1 who crossed over to vimseltinib in Part 2, will have as their reference day the first dose date of vimseltinib in Part 2, and their data from Part 1 while receiving placebo will be excluded.

9.11.1. Extent of Treatment Exposure

Descriptive summaries will be provided by treatment group for the following variables for the SAF:

- Treatment duration (weeks), calculated as (date of last dose date of first dose + 1)/7
- Number of cycles initiated
- Total dose received, defined as the sum of the actual doses (mg) administered
- Total planned dose (mg), defined as the sum of the prescribed doses (mg)
- Average weekly dose (mg/week), defined as total dose received (mg) / treatment duration (weeks)
- Relative dose intensity (%), defined as total dose received (mg) / total planned dose (mg) x 100
- Number of participants with drug withdrawn
- Number of participants with the following situations:
- Number of participants with dose increase
- Number of participants with dose reduction
- Number of participants with dose interruption
- Number of participants with missed dose

Treatment exposure will be listed for the SAF.

9.11.2. Adverse Event

Adverse events (AEs) will be coded using MedDRA version 26.0 (or higher). The intensity of AE will be documented using the National Cancer Institute (NCI) Common Terminology Criteria for Adverse Event (CTCAE) version 5.0.

A treatment-emergent AE (TEAE) is defined as any AE that occurs or worsens after administration of the first dose of study drug and through 30 days after the last dose of study drug or the day before the start of new antitumor therapy. Drug-related AEs reported after 30 days following the last dose of study drug will also be considered as treatment-emergent.

Drug related AEs include AEs reported as 'POSSIBLY RELATED' and 'RELATED'.

Summary statistics (frequency and percentages of participants) will be presented by SOC and PT by treatment group for following:

- Overall summary of TEAEs
- Any TEAE
- Any nonserious TEAE
- Any Grade 3/4 TEAE
- Any serious TEAE

- Any drug-related TEAE
- Any Grade 3/4 drug-related TEAE
- Any drug-related serious TEAE
- Any TEAE leading to dose modification (including dose reduction and interruption)
- Any drug-related TEAE leading to dose modification (including dose reduction and interruption)
- Any TEAE leading to treatment discontinuation
- Any drug-related TEAEs leading to treatment discontinuation
- Any TEAE leading to death

The following will be tabulated by SOC, PT, and maximum severity grade:

- TEAEs
- Serious TEAEs
- Drug-related TEAEs
- Drug-related serious TEAEs

The following will be presented by PT:

- TEAEs
- TEAEs of Grade 3/4
- Serious TEAEs
- Drug-related TEAEs
- Drug-related TEAEs of Grade 3/4
- Drug-related serious TEAEs

If a SOC or PT was reported more than once for a participant, the participant would only be counted once in the incidence for that SOC or PT. For participants experiencing the same PT at multiple severity levels, the occurrence of the AEs with the maximum severity will be counted in the analysis of incidence by severity. For participants experiencing the same PT at multiple relationship levels, the occurrence of the AEs with the strongest relationship to study drug will be counted in the analysis of incidence by relationship to study drug.

The following listings will be provided for the SAF:

- All AEs (including AEs occurring prior and after the TEAE period)
- Serious Adverse Events
- Death
- AEs leading to study drug discontinuation
- AEs leading to dose modification (reduction or interruption)

9.11.3. Clinical Laboratory Tests

The following laboratory parameters will be summarized:

Hematology	Serum Chemistry	Coagulation	Urinalysis (dipstick) ^a
Hematocrit Hemoglobin Platelet count Red blood cell count WBC with differential	Alanine aminotransferase Albumin Alkaline phosphatase Aspartate aminotransferase Bicarbonate Calcium Cholesterol Chloride Creatinine Gamma-glutamyl transferase Glucose Potassium Sodium Magnesium Phosphorus Total bilirubin Conjugated (direct) bilirubin Unconjugated (indirect) bilirubin ^b Total protein Triglycerides Urea (blood urea nitrogen)	Activated partial thromboplastin time Prothrombin time International Normalized Ratio	Hemoglobin Glucose Ketone Protein Specific gravity

^a An additional microscopic examination will be performed if any dipstick analytes are 2+ or higher. A participant should undergo further assessment (eg, a 24-hour urine collection) if the protein in analyte is >=2+

^b Will be calculated by central laboratory.

Descriptive statistics (number of observations, mean, median, standard deviation, minimum, and maximum values) will be presented for clinical laboratory tests. Changes from baseline (including baseline value) by treatment group will be summarized at each scheduled visit. Graphical presentations may also be generated for specific laboratory parameters by visit and treatment group to investigate the trend over time and outliers in the data.

Abnormal laboratory results will be graded with NCI CTCAE version 5.0, if applicable. A shift table, presenting the 2-way frequency tabulation for baseline and the worst post-baseline values according to the NCI CTCAE grade, will be provided by treatment group for hematology and serum chemistry.

A Hy's law summary table and plot will be provided. A plot of alkaline phosphatase vs. total bilirubin will be provided.

A comprehensive listing of all hematology, chemistry (including CPK added in Protocol Amendment 3), coagulation, urinalysis, and pregnancy results will be provided for the SAF. The listing will include the test result, the normal range, change from baseline, and CTCAE grade. Separate listings for hematology and chemistry presenting clinically significant abnormalities or abnormalities of CTCAE grade 3 or 4 will be provided.

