9.6.3. Dose Interruption and Management of Toxicities

9.6.3.1. Guidelines for Hepatobiliary Lab Elevations

Recommended dose interruption and management of treatment-related hepatobiliary lab elevations are shown in Table 9.

Table 9:Dose Interruption and Management of Treatment-related Hepatobiliary
Laboratory Elevations

Toxicity Grade CTCAE v5.0	Dose Interruption and Management	
Grade 2 ALT and/or AST increase	Continue treatment with study drug	
(>3–5×ULN) and total bilirubin ≤ULN	Check for changes to medications and symptoms	
	Perform confirmation liver enzyme (AST, ALT and ALP) and bilirubin tests within 48-72 hours	
	Repeat liver enzyme tests weekly for 8 weeks to ensure stability	
Grade 2 ALT and/or AST increase	Hold treatment with study drug	
(>3–5×ULN) and total bilirubin	Check for changes to medications and symptoms	
increase up to 2×ULN	Perform confirmation liver enzyme (AST, ALT, and ALP) and bilirubin tests within 48-72 hours	
	Repeat liver enzyme tests weekly	
OR	Study drug may be resumed at 1 dose level reduction once Hy's law has been definitively ruled out, labs resolve to Grade 1 or baseline, after discussion with Sponsor	
Total bilirubin increase up to 2 ×ULN	If ALT/AST/bilirubin continue to increase, or the increased level persists more than 28 days:	
	Discontinue study drug	
	Refer for gastroenterology/hepatology consultation	
	Consider liver ultrasound	

Toxicity Grade CTCAE v5.0	Dose Interruption and Management		
Grade 2 ALT and/or AST increase	Hold treatment with study drug		
(>3–5×ULN) and total bilirubin	Check for changes to medications and symptoms		
increase >2×ULN or INR >1.5 and ALP <2×ULN	Perform confirmation liver enzyme (AST, ALT and ALP), bilirubin, and INR tests within 48-72 hours		
	Refer for gastroenterology/hepatology consultation		
OP	Consider liver ultrasound		
OR	Repeat liver enzyme, bilirubin, and INR tests weekly until resolution to Grade 1 or baseline		
Total bilirubin increase >2×ULN	Study drug may be resumed at 1 dose level reduction once Hy's law has been definitively ruled out, labs resolve to Grade 1 or baseline, after discussion with Sponsor		
	If ALT/AST/bilirubin/INR continue to increase , or the increased level persists more than 28 days:		
	Discontinue study drug		
Grade 3 ALT and/or AST increase	Hold treatment with study drug		
(>5–8×ULN) and total bilirubin \leq ULN	Check for changes to medications and symptoms		

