11.9.14.2. Clinical Laboratory Tests for Safety

Clinical laboratory tests are summarized in Table 14 and will be performed by a central laboratory, except for urinalysis, according to the relevant schedule of assessments. Additional (unscheduled) local laboratory samples for safety or repeat tests may be collected, if clinically indicated.

All laboratory test results that are abnormal and considered clinically significant must be reported as AEs (Section 11.9.14.3.1). If a clinically significant laboratory AE is supported by a corresponding local lab result, but not by the central lab result, the local lab result will be recorded. All samples will be collected in accordance with acceptable laboratory procedures and graded for toxicity as defined by the National Cancer Institute (NCI)-CTCAE, v5.0.

Available local laboratory test results should be used for treatment management decisions and initial assignment of CTCAE grading. Every effort should be made to discuss any changes to study drug dosing with the Sponsor before implementation, and only if not feasible beforehand, to inform the Sponsor within the same day. Central laboratory results will be used for final assignment of CTCAE grading. In the case of different grades associated with local versus central laboratory results for AEs, the Investigator should determine which laboratory values will be used to document grading of AEs. The local vs central laboratory result with the highest grade should be considered to document grading of AEs.

Hematology	Coagulation	Chemistry	Urinalysis (dipstick) ^a
Hematocrit	Activated partial	Alanine	Hemoglobin
Hemoglobin	thromboplastin time	aminotransferase	Glucose
Platelet count	Prothrombin time	Albumin	Ketone
Red blood cell count	International	Alkaline phosphatase	Protein
White blood cell count with differential	normalized ratio	Aspartate aminotransferase	Specific gravity
		Bicarbonate	
		Calcium	
		Cholesterol	
		Chloride	
		Creatine phosphokinase	
		Creatinine	
		Gamma-glutamyl transferase	
		Glucose	
		Potassium	
		Sodium	
		Magnesium	
		Phosphorus	
		Total bilirubin	
		Conjugated (direct) bilirubin	
		Unconjugated (indirect) bilirubin ^b	
		Total protein	
		Triglycerides	
		Blood urea nitrogen	

Table 14: Clinical Laboratory Tests

^a An additional microscopic examination will be performed if any dipstick analytes are 2+ or higher. A participant should undergo further assessment (eg, a 24-hour urine collection) if the protein analyte is \geq 2+.

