12.4.6. Safety Analyses

Participants from the Safety Set will be included in safety analyses.

AEs will be coded using the MedDRA for purposes of summarization. All AEs occurring on study will be listed in by participant data listings. Treatment-emergent AEs will be tabulated, where treatment emergent is defined as any AE that occurs after administration of the first dose of study drug and through 30 days after the last dose of study drug. Tabulations for all TEAEs, treatment-emergent SAEs, related TEAEs, dose reduction, dose interruptions, and discontinuation of study drug due to AE will be produced. By participant listings will be provided for deaths, SAEs, and AEs leading to discontinuation of study drug.

Change from baseline in clinical laboratory parameters will be summarized across time on study, and the frequency of clinically significant abnormal laboratory values will be tabulated.

Changes in ECG intervals (QT, RR, QTcF, HR, QRS) and vital sign parameters (including systolic and diastolic blood pressure, heart rate, respiration rate, and temperature) will be summarized over time in a similar fashion to laboratory parameters, and any abnormal values will be tabulated. Changes in ECG findings will be presented in data listing format.

Additional safety assessments such as ECGs will be listed by participant.

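### SAP 9.11.3 plans no worst post-baseline tabulation by arm for coagulation or dipstick urinalysis, so no output guarantees a count of participants with INR >1.5 or dipstick 2+ or higher

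*SAP*

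**What the plan says.** SAP 9.11.3 lists four laboratory panels: hematology, serum chemistry, coagulation (aPTT, PT, INR) and dipstick urinalysis (hemoglobin, glucose, ketone, protein, specific gravity). For all of them, "Descriptive statistics (number of observations, mean, median, standard deviation, minimum, and maximum values) will be presented for clinical laboratory tests", and "Changes from baseline (including baseline value) by treatment group will be summarized at each scheduled visit". Grading is not limited by panel: "Abnormal laboratory results will be graded with NCI CTCAE version 5.0, if applicable". The listing is also complete: "A comprehensive listing of all hematology, chemistry (including CPK added in Protocol Amendment 3), coagulation, urinalysis, and pregnancy results will be provided for the SAF".

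Outputs that isolate abnormal values are narrower. The two-way table of baseline against worst post-baseline value, "according to the NCI CTCAE grade, will be provided by treatment group for hematology and serum chemistry", leaves out coagulation and urinalysis. So do the separate listings of clinically significant or Grade 3/4 values. A Hy's law table and plot are planned, but their criteria are not given.

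The protocol attaches actions to both omitted panels. In Protocol 9.6.3.1, Table 9, one Grade 2 ALT/AST row is defined by a bilirubin "increase >2×ULN or INR >1.5 and ALP <2×ULN", and a Grade 3 ALT/AST row also uses INR >1.5. For urine, a footnote to Table 14 in Protocol 11.9.14.2 says: "An additional microscopic examination will be performed if any dipstick analytes are 2+ or higher". Protein at that level also calls for further assessment.

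On reporting, Protocol 12.4.6 says that "the frequency of clinically significant abnormal laboratory values will be tabulated". It names no excluded panel.

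**The concern.** A safety reader will want to know how many participants in each arm ever crossed a threshold that the protocol acts on, and for INR whether that happened alongside raised transaminases. By-visit summaries do not answer this. They describe one value per participant per visit, and a visit maximum shows that someone was high, but not how many were or whether ALT or AST was raised in the same person. For the dipstick tests that are read as ordered categories, a mean and SD have no useful meaning.

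The question is relevant here. Protocol 5.1 cites liver injury that can be fatal with the approved CSF1R inhibitor, and Table 9 uses INR to separate levels of liver management. The SAP does use threshold counts elsewhere: SAP 9.11.4 reports QTcF above 450, 480 and 500 msec.

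**Working it through.** The plan states no figure to reproduce. The check is an inventory of outputs, followed by a test of each route that might supply the count.

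**Size of the omitted group.** Entries in the SAP 9.11.3 table: 5 hematology + 21 chemistry + 3 coagulation + 5 urinalysis = 34. Entries without a worst-value table: 3 + 5 = 8. This counts table entries, with the white-cell differential as part of one entry. It does not measure impact.

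**Planned outputs by panel (SAP 9.11.3).**

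| Output | Hematology, chemistry | Coagulation, urinalysis |
|---|---|---|
| n, mean, median, SD, min, max by visit | yes | yes |
| Change from baseline by arm and visit | yes | yes |
| Full listing with CTCAE grade | yes | yes |
| Baseline-to-worst shift table by arm | yes | no |
| Listing of clinically significant or Grade 3/4 values | yes | no |
| Table at INR >1.5 or dipstick 2+ | not applicable | none named |

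**Routes that might still give a by-arm count.**

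1. *By-visit maximum.* It shows that at least one analyzed value exceeded 1.5 at that visit. It gives no number of participants and no link to ALT/AST.
2. *Adverse events.* Protocol 11.9.14.2 requires clinically significant abnormal results to be reported as adverse events, and SAP 9.11.2 counts these by preferred term and arm. However, Protocol 11.9.14.3.8.1 leaves significance to the investigator and prefers a diagnosis to a bare test result, so a raised INR during a liver event may be coded under the liver diagnosis.
3. *Categorical rule in SAP 9.1.* Frequencies and proportions could be applied to dipstick results visit by visit. That gives no worst-value count per participant, and does nothing for INR, which is numeric.
4. *Hy's law table.* Its contents are unspecified, so INR can be neither assumed in it nor excluded from it.

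**What happens to repeat INR tests.** Table 9 asks for repeat INR within 48-72 hours and then weekly in the Grade 2 row, or at least twice weekly in the Grade 3 row. Under SAP 8.3, by-visit summaries use the nominal visit, and unscheduled results are mapped by midpoint windows. Among several unscheduled results in a window, the one closest to the target day is used.

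As an illustration, assume visits fall on target and the Grade 2 row is triggered at Cycle 3 Day 1:

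- Target days with 28-day cycles: Cycle 2 = 29, Cycle 3 = 57, Cycle 4 = 85, Cycle 5 = 113.
- Cycle 3 window: (29 + 57)/2 = 43 to (57 + 85)/2 = 71.
- Cycle 4 window: 71 to (85 + 113)/2 = 99.
- Repeats: 57 + 2 or 3 = Day 59-60, then weekly from Day 57 at Days 64, 71 and 78.

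Days 59-60 and 64 lie inside the Cycle 3 window, Day 71 is on the boundary, and Day 78 lies in the Cycle 4 window. Each window already holds a scheduled result on its target day. Whether the nominal visit takes priority or the closest value is chosen, the scheduled result is kept. An INR peak at Day 64 would then appear in the listing but not in the by-visit mean or maximum.

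SAP 8.4.1 lets unmappable results feed worst-case values where applicable, but no worst-case output is planned for coagulation. SAP 9.11 also takes the central result when local and central results share a nominal visit, while Protocol 11.9.14.2 allows unscheduled repeats to be local.

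**Protocol against SAP.** Protocol 12.4.6 promises a frequency tabulation of clinically significant laboratory abnormalities. SAP 9.11.3 names no such table. It offers a graded shift table for two panels, plus listings. SAP 1 gives the SAP precedence and says differences will be highlighted in Section 11. SAP 11 reports no major changes.

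**The case against.** A reader might infer that coagulation and urinalysis get only means, so that a single high INR would be invisible. The documents do not support that. Median, SD, minimum and maximum are planned, graphs to look for outliers are allowed, and the listing carries normal range and CTCAE grade. A high scheduled value would show as the visit maximum. What is missing is a participant count.

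A reader might also infer that these abnormalities are never counted by arm. That is too strong. Under Protocol 11.9.14.3.8.1, a result that needs further diagnostic testing, or leads to a hold or stop of study drug, counts as clinically significant. A 2+ dipstick prompts further testing, and the Table 9 rows containing INR >1.5 involve a hold or discontinuation. Many such cases should therefore reach the by-arm adverse event tables, and dipstick frequencies by visit may follow from SAP 9.1. Neither route guarantees a threshold count.

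Three further points limit the weight of the concern:

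- INR >1.5 is never a stand-alone trigger in Table 9. It acts only with Grade 2 or Grade 3 ALT/AST, and those participants already appear in the chemistry shift table. Dipstick 2+ prompts further testing and is not a dosing rule.
- The liver warning in Protocol 5.1 concerns another drug. Protocol 5.2 reports that transaminase elevations with vimseltinib came without bilirubin elevation and/or other signs of liver damage.
- The SAP's silence does not clearly cancel the Protocol 12.4.6 tabulation. That sentence concerns clinically significant values, so it does not itself promise a count at INR 1.5.

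All three stand. They make the point minor. They do not supply the missing tabulation.

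**Conclusion.** The concern holds as a minor safety-reporting gap. For 8 of 34 laboratory entries the SAP defines no worst post-baseline tabulation by arm, and no planned output guarantees the number of participants with INR >1.5, with INR >1.5 plus raised ALT/AST, or with dipstick 2+ or higher. Adverse event tables and by-visit frequencies close part of the gap. The visit-window rules leave a further weakness, because the repeat INR tests ordered during a liver event are the ones most likely to miss the by-visit summaries.

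The SAP also does not show how Protocol 12.4.6 is met for these panels. This reads as an unreconciled wording gap and gives no ground for inferring a deliberate withdrawal.

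The conclusion assumes that the Hy's law table, whose criteria are not stated, does not already include INR. If it does, the INR part shrinks accordingly. No data go uncollected or unlisted, and the efficacy analyses are unaffected.

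**What to change.** In SAP 9.11.3:

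1. Extend the baseline-to-worst shift table to coagulation where a CTCAE grade applies, and state that unscheduled results count towards the worst value.
2. For dipstick tests read as categories, replace mean, SD and change with a by-arm table of worst post-baseline category, showing the number at 2+ or higher for each analyte.
3. State the Hy's law criteria and add to that summary the number of participants by arm with INR >1.5 at any time after baseline, and with INR >1.5 together with ALT or AST >3×ULN.

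If the sponsor prefers not to add these tables, SAP 11 should at least say how the Protocol 12.4.6 tabulation is met, or why it is omitted, for coagulation and urinalysis.

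The cost is a short SAP edit and two or three extra safety tables from data already collected. The counts use thresholds already in the protocol, and no clinical rule changes.
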